### 3.4 Objective 3, 6 (exploratory) and 7 (exploratory) Methods

[figure not shown]
***Study design:*** Prospective longitudinal cohort study of CMV infected and uninfected neonates

***Study participants:*** The cohort will consist of newborn infants identified as laboratory confirmed CMV infected from objective 2 forming the cases and a subset of neonates identified as CMV uninfected at birth chosen as controls. Each case will be matched to 2 controls by age, gestational age at birth ( $\pm 2$  weeks) and HIV exposure. Within 2 weeks of age, cases and controls will be recalled to the site to consent for follow up and initiation of investigations as illustrated in figure 2.

***Data collection:*** Postnatal CMV acquisition: A saliva and urine sample from each control infant will be collected at the 2 weeks visit. At subsequent follow up visits, infant saliva and urine will be collected from those that tested CMV negative at the preceding visit.

Incidence of neurological sequelae: neurological sequelae is one or more of: unilateral or bilateral SNHL, developmental deficit, unilateral or bilateral ocular abnormality, abnormal cerebral imaging, microcephaly, or seizures not related to an acute systemic infection or CNS insult (refer to [Appendix 11](#) for case definition of each sequela).

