**Clinical significance and long term outcome of congenital CMV:** Most newborns with congenital CMV are asymptomatic at birth (85-90%). Of the 10-15% of symptomatic newborns clinical manifestations range from mild, non-specific findings to multi-organ system involvement. The most frequent signs are petechiae, jaundice and hepatosplenomegaly. Central nervous system (CNS) signs include microcephaly, hearing impairment, chorioretinitis and/or

optic atrophy and seizures. Of the symptomatic neonates, about 50% are small for gestational age, 33% are born prematurely and 5% die in the neonatal period.

Permanent neurological sequelae occurs in 40-58% of symptomatic and 14% of asymptomatic infants at birth. Children with symptomatic birth infection may have multiple neurological sequelae including SNHL (30-60%), cerebral palsy and mental retardation (50-80%) visual impairment (20-35%) and neurodevelopmental behaviour disorders (30-60%). The most common sequela in infants asymptomatic at birth are SNHL (10%) with other complications occurring at a lower frequency: motor deficits (5%) and chorioretinitis (2%).

**Effect of HIV:** An estimated 3% of congenital CMV infection occurs in HIV exposed infants compared to 1% in HIV unexposed infants. HIV infected infants have an even higher prevalence of congenital CMV (10.3%) as found in a French perinatal cohort. In this study, HIV and CMV co-infected newborns had a 3-fold greater risk of symptomatic congenital CMV infection at birth (23%) than HIV exposed but uninfected infants (6.7%). CMV co-infection may also contribute to HIV disease progression with increased risk of mortality and faster progression of CNS disease in survivors. However, the incidence of vertical CMV transmission in HIV infected women decreased following introduction of antiretroviral therapy (ART) during pregnancy.

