Data on congenital CMV infection among HIV exposed infants in sub-Saharan Africa are limited. A Kenyan study of infants born to mothers on perinatal Zidovudine, identified congenital CMV rates of 29% (4/14) in HIV-infected infants and 2.7% (1/37) in HIV exposed but uninfected infants. Zambian newborns admitted to a referral neonatal unit had a congenital CMV prevalence of 3.8% (15/395) whilst prevalence in HIV exposed newborns was 11.4% (9/79). Although HIV prevalence in South African pregnant women is one of the highest in the world (29.9%), a single study has evaluated the relationship between congenital CMV and HIV exposure. In Cape Town, Manicklal et al (2013) found a congenital CMV prevalence of 2.9% (22) in 748 HIV exposed babies. Maternal CD4+ count <200 cells/µL was independently

associated with congenital CMV. Clinical outcomes in these infants and prevalence of congenital CMV among HIV unexposed newborns were not investigated.

**Perinatal and Postnatal CMV infection:** Perinatal CMV infection is defined as CMV infection after 22 completed weeks (154 days) of gestation and seven completed days after birth. Postnatal CMV acquisition is CMV infection acquired any time after birth through consumption of breast milk from CMV seropositive, lactating mothers is common. Most term infants with perinatal CMV infection are asymptomatic, as maternally transferred CMV IgG antibody provides adequate protection against disease. However, studies have identified a significant risk for low-birth-weight (LBW), premature infants for the development of CMV disease such as pneumonia, hepatitis or sepsis-like illness. Data on severity and incidence of disease and long term impact in these infants is currently lacking requiring further study.

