**Figure 1: Data collection process for Objectives 1, 2 and 5**

All children with any clinical finding are referred to the neonatology department at CHBAH for clinical management as per standard of care. If a newborn PCR indicates CMV infection, the mother will be contacted telephonically to return to the site within two weeks of birth. At this visit the implications of the positive CMV result will be explained and additional consent for the continued follow up of the child (refer to [Appendix 7](#) for ICF and [Appendix 8](#) for schedule of study visits). Should consent be confirmed, a second saliva swab and a urine sample will be collected for PCR to confirm CMV infection. Babies that test CMV negative on both the second saliva swab and urine will not be enrolled as a case as the saliva positivity may be a result of CMV infected breast milk contamination. However, they will be referred for hearing screening as standard of care. Cases testing positive on both saliva and urine or urine alone will continue as cases for objective 3.

Mothers of CMV cases will have a vaginal swab and breast milk collected for quantitative PCR by a research nurse or the investigator. A subset of mothers that tested seropositive for CMV but gave birth to CMV uninfected neonates will also be recalled as controls for the case mothers in a

1:1 ratio, matched by HIV infection, for vaginal fluid and breast milk collection within 2 weeks of delivery.

**Sample size:** Objective 1: Assuming the estimated CMV prevalence is 86% in pregnant women 200 mothers will be needed to estimate the true value with a desired precision of 5% and confidence interval of 95%.

Objective 2: Prevalence of congenital CMV in HIV exposed neonates is 2.9% and in unexposed neonates is 1.0%. Thus, a total sample of 1662 neonates with 831 HIV exposed and 831 unexposed (1:1 ratio) for 80% power, are required to detect a 2.9 fold difference in CMV prevalence between the 2 groups. This will be increased to 2160 neonates, to accommodate objective 3, to determine clinical sequelae in CMV infected infants ([section 3.3.1, Sample size](#)). After adjusting for 10% being non-evaluable, 1077 HIV exposed (providing 31 CMV infected) and 1077 HIV unexposed infants (providing ~11 CMV cases) are required. Ranges of sample size estimates for varying CMV prevalences by HIV exposure are given in [Appendix 9](#).

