**Figure 2: Schedule of study visits and follow up investigations**

Mothers will receive a reminder phone call 1 week prior to each visit. Cranial ultrasonography will be conducted at the neonatology unit and fundoscopic examination at St. John's eye hospital. Hearing screening will be conducted at the audiology department as per standard of care by automated auditory brainstem evoked response audiometry (AABR). Developmental assessment will be performed by myself at the research clinic through a developmental assessment tool (Ages and stages questionnaire or Bayley III scales of infant and toddler development or equivalent). Refer to [Appendix 12](#) for list of follow up data. Standard operating procedures to ensure standardisation of assessments between assessors will be developed.

Blinding of the assessors to the status of CMV infection will be maintained at each assessment. If impairments requiring clinical management are identified, the assessor will be provided with the laboratory data. Any impaired infant will be referred to specialist CHBAH paediatric clinics for clinical management. HIV-exposed infants are tested for HIV-infection by PCR at birth, 6 weeks of age and again at least 3 months post breast-feeding cessation, as per standard of care in South Africa. Should a child test HIV-infected, they will be referred to the HIV clinic at CHBAH.

Infant specific vaccine induced immune responses: Cases and controls identified will be vaccinated as per the immunisation schedule in South Africa with hexavalent DTaPHibHepBIPV at 6, 10 and 14 weeks and PCV and rotavirus vaccine at 6 and 14 weeks of age. Mothers will be encouraged to access vaccines at the vaccination clinic at RMPRU and counselled on ensuring their infants are vaccinated at the scheduled time. At the 3rd study visit when infants are aged 6 months a venous blood sample will be collected by appropriately trained study staff. The volume of blood collected will be not more than 5ml following the recommendations by HREC (medical) on blood volumes from paediatric research participants.

**Laboratory** Venous blood will be centrifuged and aliquots of serum will be stored at -70°C.

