Antibody to diphtheria toxoid, tetanus-toxoid, pertussis toxoid, filamentous hemagglutinin (FHA) and hepatitis B surface antigen (HBsAg) will be measured by an in-house Luminex multiplex immunoassay. Immune responses to the primary series of PCV will be measured by a standardized enzyme immunoassay (EIA) to test for vaccine serotype-specific capsular immunoglobulin (Ig) G antibody concentrations and opsonophagocytic assay. Titres of rotavirus-specific IgA will be determined in enzyme-linked immunosorbent assays. Refer to appendix 10 for the serological correlates of protection .

**Sample size:** The anticipated prevalence of neurological sequelae in CMV uninfected controls with uneventful foetal or perinatal periods is estimated at 1%. Prevalence of neurological sequelae in CMV infected infants is expected to be higher at approximately 17%. For 80% power, the difference that could feasibly be detected, is 17-fold i.e. 1% vs 17%. Allowing for a loss to follow up of 10%, 42 CMV infected infants and 84 controls (n=126) with an allocation ratio of 1:2 are required ([Appendix 9](#)).

**Data Analysis:** Table 3 describes the data analysis plan to determine the incidence and risk factors for neurological sequelae in congenital CMV infected infants

Table 3: Data analysis plan

Objective 3  Incidence calculation of one or more neurological sequelae for cases and controls at 2 weeks, 2 months, 6 months and 12 months of age dependent on investigations done at each visit  Comparison of proportions with permanent sequelae (hearing impairment and developmental deficit) at each visit between cases and controls using a Z test to compare ratios, including 95% confidence intervals.  Adjust for potential confounders (IUGR, symptoms at birth, gender and co-morbidities) by multiple logistic regression analysis to establish factors contributing to neurological sequelae.
Objective 6  Incidence of postnatal acquisition of CMV in newborns will be calculated at 2 months, 6 months and 1 year of chronological age. Incidence of neurological sequelae in postnatally infected infants will be calculated
Objective 7

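### Objective 3 matches controls on HIV exposure but not on infant HIV infection, and the analysis does not name it, so any impairment caused by HIV is credited to CMV: an upward bias, probably modest

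*Combined protocol and SAP*

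**What the plan says.** **Matching.** Section 3.4 (Study participants) states: "Each case will be matched to 2 controls by age, gestational age at birth", within 2 weeks, "and HIV exposure. Within 2 weeks of age, cases and controls will be recalled to the site to consent for follow up". The only HIV criterion is exposure, so HIV-infected and exposed-uninfected infants count as the same stratum.

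**Analysis.** The table for Objectives 3, 6 and 7 in section 3.4 (the second of two tables numbered 3) compares proportions with hearing impairment or developmental deficit at each visit by a Z test with no adjustment. It then says: "Adjust for potential confounders (IUGR, symptoms at birth, gender and co-morbidities) by multiple logistic regression analysis". Infant HIV infection is not named. Objective 4 (section 3.5, Data analysis) does name HIV infection and exposure, and lists co-morbidity as a separate item.

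**Available data.** The text under Figure 2 says: "HIV-exposed infants are tested for HIV-infection by PCR at birth, 6 weeks of age", and again after breast-feeding stops. The only stated use is referral to the HIV clinic.

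**Background.** Section 1.2 reports: "HIV infected infants have an even higher prevalence of congenital CMV (10.3%) as found in a French perinatal cohort". A Kenyan study "identified congenital CMV rates of 29% (4/14) in HIV-infected infants and 2.7% (1/37) in HIV exposed but uninfected infants". The planning value in section 3.3 is: "Prevalence of congenital CMV in HIV exposed neonates is 2.9"%.

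**The concern.** Objective 3 is meant to show what congenital CMV does to neurological outcome. If HIV-infected infants are over-represented among cases, and HIV itself causes some developmental deficit, those events are counted as CMV events with few counterparts among the controls. Matching on exposure cannot prevent this, because the imbalance arises within the exposed stratum, which supplies about 31 of the 42 expected cases.

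Only about 7 case events are expected (0.17 × 42 = 7.1) and fewer than one control event (0.01 × 84 = 0.84), so one or two misattributed events would be visible in the result. The justification in section 1.3 ties the findings to a possible targeted screening programme in HIV-exposed infants, the stratum affected.

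**Working it through.** **1. The plan's case mix.** Section 3.3 expects 1077 × 0.029 = 31.2 exposed cases and 1077 × 0.010 = 10.8 unexposed cases, about 42 in all. This reproduces. At 1:2 there are 62 exposed controls and 84 controls in total.

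**2. Share of HIV-infected infants in the exposed stratum.** Let *m* be mother-to-child HIV transmission, *a* the congenital CMV prevalence in HIV-infected infants and *b* that in exposed-uninfected infants.

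- Cases: m·a / [m·a + (1−m)·b]
- Controls: m·(1−a) / [m·(1−a) + (1−m)·(1−b)]

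The documents give *a* and *b* but not *m*, which I assume to be 1% to 5%. For *b* I use 2.9%, which strictly describes all exposed infants; using 2.7% changes little.

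Example with m = 2%, a = 10.3%, b = 2.9%:
- Cases: 0.00206 / (0.00206 + 0.02842) = 6.8%; × 31 = 2.1 infants
- Controls: 0.01794 / (0.01794 + 0.95158) = 1.85%; × 62 = 1.15 infants

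| Source of a, b | m | HIV-infected cases (of 42) | HIV-infected controls (of 84) | Ratio of shares |
|---|---|---|---|---|
| 10.3%, 2.9% | 1% | 1.1 | 0.6 | 3.7 |
| | 2% | 2.1 | 1.1 | 3.7 |
| | 5% | 4.9 | 2.9 | 3.4 |
| Kenyan 4/14, 1/37 | 1% | 3.0 | 0.5 | 13.1 |
| | 2% | 5.5 | 0.9 | 12.0 |
| | 5% | 11.1 | 2.3 | 9.6 |

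With 10.3% against 2.7%, the ratio is 3.6 to 4.0. The ratio barely depends on *m*; the counts do.

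**3. Spurious risk difference.** Let *r* be the probability that HIV alone produces the outcome. The documents give no value. The difference added with no CMV effect is r × (HIV-infected cases/42 − HIV-infected controls/84).

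At r = 30% (assumed) and m = 2%:
- 10.3%/2.9%: 0.30 × (2.10/42 − 1.15/84) = 1.1 percentage points
- Kenyan: 0.30 × (5.50/42 − 0.92/84) = 3.6 points

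Across m = 1% to 5% at r = 30%, the ranges are 0.6 to 2.5 points and 2.0 to 7.1 points. The result is proportional to *r*. The planned difference is 17% − 1% = 16 points.

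**4. Effect on the test.** Take a 1% background rate, no CMV effect, 42 against 84 infants and r = 30%. The chance that the Z test (two-sided 5% assumed) declares more impairment in cases rises from 2.9% to 6–15% on 10.3%/2.9%, or to 16–47% on the Kenyan figures, over m = 1% to 5%.

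**The case against.** **The magnitude rests on outside inputs.** Neither the transmission rate nor an HIV-only impairment rate is in the documents. This stands: the direction follows from the protocol's figures, the size does not.

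**The prevalences are thin.** The 10.3% and the 2.7% to 2.9% come from different studies. The one within-study contrast is 4/14 against 1/37, with exact 95% intervals of 8% to 58% and 0.07% to 14%, in mothers given perinatal zidovudine. Section 1.2 adds that vertical CMV transmission in HIV-infected women fell after antiretroviral therapy in pregnancy. The upper range is therefore a bound, not a planning value.

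**The CNS evidence.** Section 1.2 associates co-infection with "increased risk of mortality and faster progression of CNS disease in survivors". A reader might infer that HIV alone causes the impairment counted here. The sentence is about CMV worsening HIV disease, which is arguably part of the CMV effect, so it does not support that inference.

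**The tested outcome is narrower.** The Z test covers hearing impairment and developmental deficit. Microcephaly and abnormal imaging enter only the incidence of the composite. This stands, and limits the bias in the test mainly to developmental deficit.

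**Co-morbidities might include HIV.** The term is undefined, and the appendices with case definitions and follow-up data are not in the text. But Table 2 and section 3.5 list HIV apart from co-morbidities, and a model covariate would not correct an unadjusted Z test.

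**Exposure is a practical matching factor.** Recall is within 2 weeks of birth, when only the birth PCR could be available. This is fair, and is why the remedy belongs in the analysis and not in the matching.

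**Conclusion.** The gap is real. Followed as written, Objective 3 neither balances nor adjusts by name for infant HIV infection, which the protocol's own prevalences make about 3 to 4 times, possibly 10 or more times, as common among exposed cases as among their controls. The bias is upward if HIV alone causes any of the measured impairment.

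Its size is probably modest. On the 10.3% figure it involves about 1 to 5 HIV-infected cases against 0.6 to 3 controls, and at most about 11 against 2 on the Kenyan figures. Both ranges assume 1% to 5% transmission.

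Two stronger readings are not supported:
- **That HIV could account for the planned contrast.** With 20% to 40% HIV-only impairment and 1% elsewhere, a null risk ratio of about 1.3 to 5.5 can be computed. It looks large because it sits on a 1% base. In absolute terms, at 30% it is 0.6 to 7.1 points, against the planned 16.
- **That HIV-infected infants must leave the main comparison.** They belong to the HIV-exposed population that section 1.3 addresses, and removing them would change the target population.

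**What to change.** In the Objective 3 analysis plan in section 3.4:

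1. Use the standard-of-care infant HIV PCR results to tabulate sequelae in cases and controls by infant HIV status: unexposed, exposed-uninfected, infected. State which PCR results define the status, since the post-breast-feeding test comes later than the other two.
2. Name infant HIV infection as a term in the logistic model, as Objective 4 already does.
3. Prespecify a repeat of the case-control comparison excluding HIV-infected infants, reported beside the all-infant result. Keep all infants in the main comparison.

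**Cost.** Protocol wording and a little analysis; the PCRs are already done. With about eight events expected in total, the HIV term will be imprecise and may not be estimable, so the table and the restricted comparison carry most of the information. The restricted comparison is less precise. Of 42 cases about 38 remain after the planned 10% loss. Removing 6 leaves 32, with power about 0.80 for 1% against 17% (1:2, two-sided 5%, no continuity correction); removing 11 leaves 27, with power about 0.74. This is a reason to present it as a supporting analysis.

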**Figure 2: Schedule of study visits and follow up investigations**

Mothers will receive a reminder phone call 1 week prior to each visit. Cranial ultrasonography will be conducted at the neonatology unit and fundoscopic examination at St. John's eye hospital. Hearing screening will be conducted at the audiology department as per standard of care by automated auditory brainstem evoked response audiometry (AABR). Developmental assessment will be performed by myself at the research clinic through a developmental assessment tool (Ages and stages questionnaire or Bayley III scales of infant and toddler development or equivalent). Refer to [Appendix 12](#) for list of follow up data. Standard operating procedures to ensure standardisation of assessments between assessors will be developed.

Blinding of the assessors to the status of CMV infection will be maintained at each assessment. If impairments requiring clinical management are identified, the assessor will be provided with the laboratory data. Any impaired infant will be referred to specialist CHBAH paediatric clinics for clinical management. HIV-exposed infants are tested for HIV-infection by PCR at birth, 6 weeks of age and again at least 3 months post breast-feeding cessation, as per standard of care in South Africa. Should a child test HIV-infected, they will be referred to the HIV clinic at CHBAH.

Infant specific vaccine induced immune responses: Cases and controls identified will be vaccinated as per the immunisation schedule in South Africa with hexavalent DTaPHibHepBIPV at 6, 10 and 14 weeks and PCV and rotavirus vaccine at 6 and 14 weeks of age. Mothers will be encouraged to access vaccines at the vaccination clinic at RMPRU and counselled on ensuring their infants are vaccinated at the scheduled time. At the 3rd study visit when infants are aged 6 months a venous blood sample will be collected by appropriately trained study staff. The volume of blood collected will be not more than 5ml following the recommendations by HREC (medical) on blood volumes from paediatric research participants.

**Laboratory** Venous blood will be centrifuged and aliquots of serum will be stored at -70°C.

Antibody to diphtheria toxoid, tetanus-toxoid, pertussis toxoid, filamentous hemagglutinin (FHA) and hepatitis B surface antigen (HBsAg) will be measured by an in-house Luminex multiplex immunoassay. Immune responses to the primary series of PCV will be measured by a standardized enzyme immunoassay (EIA) to test for vaccine serotype-specific capsular immunoglobulin (Ig) G antibody concentrations and opsonophagocytic assay. Titres of rotavirus-specific IgA will be determined in enzyme-linked immunosorbent assays. Refer to appendix 10 for the serological correlates of protection .

**Sample size:** The anticipated prevalence of neurological sequelae in CMV uninfected controls with uneventful foetal or perinatal periods is estimated at 1%. Prevalence of neurological sequelae in CMV infected infants is expected to be higher at approximately 17%. For 80% power, the difference that could feasibly be detected, is 17-fold i.e. 1% vs 17%. Allowing for a loss to follow up of 10%, 42 CMV infected infants and 84 controls (n=126) with an allocation ratio of 1:2 are required ([Appendix 9](#)).

**Data Analysis:** Table 3 describes the data analysis plan to determine the incidence and risk factors for neurological sequelae in congenital CMV infected infants

Table 3: Data analysis plan

Objective 3  Incidence calculation of one or more neurological sequelae for cases and controls at 2 weeks, 2 months, 6 months and 12 months of age dependent on investigations done at each visit  Comparison of proportions with permanent sequelae (hearing impairment and developmental deficit) at each visit between cases and controls using a Z test to compare ratios, including 95% confidence intervals.  Adjust for potential confounders (IUGR, symptoms at birth, gender and co-morbidities) by multiple logistic regression analysis to establish factors contributing to neurological sequelae.
Objective 6  Incidence of postnatal acquisition of CMV in newborns will be calculated at 2 months, 6 months and 1 year of chronological age. Incidence of neurological sequelae in postnatally infected infants will be calculated
Objective 7

The magnitude of specific antibody response between cases and controls will be compared using the unpaired t test when data are normally distributed. In the scenario that the distribution is non-normal the Mann-Whitney test will be used instead. Normality will be tested using the Shapiro-Wilk test, where the assumption of non-normal data will be concluded based on a significant result. Frequency plots and P-P plots will also be used to confirm the normality assumption, or not.

Simple correlations will be assessed using Pearson or Spearman correlation in the case of normal or non-normal distribution, respectively. The resulting correlation coefficient will indicate the strength of association, whereas the significance test will provide the evidence of a linear correlation or not in the population.

**Potential challenges:** To account for loss to follow up and timely completion of investigations, a window period of 30 days is allowed from the date of each scheduled visit in which to perform the investigations. Transport costs will be reimbursed with R150 per scheduled visit and all investigations will be provided at no cost. Neurological sequelae in congenital CMV infected children may manifest beyond 12 months of age and long term follow up to 6 years is recommended. Hence, it is possible that this study may not detect all sequelae by 12 months of age and no differences may be observed between the 2 groups.

Parents may be reluctant to consent to a blood draw at 6 months of age and will be thoroughly counselled on the purpose and processing of the blood samples. The informed consent form has been amended to include the purpose of the blood draw and each mother will be given a new consent form to sign with the option of refusing to participate in the blood draw but continue with the rest of the study procedures.

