## 1 Introduction

Cytomegalovirus (CMV) infection is the most common congenital infection worldwide and the leading cause of non-genetic sensorineural hearing loss (SNHL)\* in childhood. Global prevalence of congenital CMV infection is estimated at 0.64%, varying across countries (0.2 – 6%) with higher prevalence's in lower and lower- middle income countries (LMIC). Seventeen percent of all infected infants are at risk of permanent neurological disability. The impact of congenital CMV infection in neonates is not well recognised as it is mainly asymptomatic at birth with the inability to attribute neurological impairment in children retrospectively to *in-utero* CMV infection.

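### The 80% power for Objective 3 uses rates and an outcome that do not match the controls, the 12-month follow-up or the planned comparison

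*Combined protocol and SAP*

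**What the plan says.** Section 3.4 (Sample size) sets the rates. For controls: "CMV uninfected controls with uneventful foetal or perinatal periods is estimated at 1"%. For cases: "Prevalence of neurological sequelae in CMV infected infants is expected to be higher at approximately 17"%. It then states "For 80% power, the difference that could feasibly be detected, is 17-fold i.e. 1% vs 17"%, and after 10% loss to follow-up asks for 42 cases and 84 controls.

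The Introduction (section 1) describes the 17% in these words: "Seventeen percent of all infected infants are at risk of permanent neurological disability". No age is attached. The Synopsis gives it as an upper figure.

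Section 3.4 (Data collection) defines the outcome: "neurological sequelae is one or more of: unilateral or bilateral SNHL, developmental deficit, unilateral or bilateral ocular abnormality, abnormal cerebral imaging, microcephaly, or seizures" (the seizures item excludes acute systemic infection or CNS insult). In the analysis table for Objective 3, this composite receives an incidence calculation in each group and a confounder-adjusted logistic regression. The case-control test is narrower: "Comparison of proportions with permanent sequelae (hearing impairment and developmental deficit) at each visit between cases and controls", by a Z test with 95% confidence intervals.

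Section 3.4 (Potential challenges) says of later onset that "long term follow up to 6 years is recommended" and that "it is possible that this study may not detect all sequelae by 12 months of age", so that the groups may not differ. It cites the same source as the 17%.

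**The concern.** A power statement is only as good as the match between its assumed rates and the people, time span and outcome that will be analysed. Here each is open to question.

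- **Controls.** The 1% belongs to a low-risk group. Section 3.4 (Study participants) does not restrict controls to such infants. A control matched to a preterm case will be preterm too, and most controls will be HIV exposed.
- **Cases.** The 17% has no age limit, whereas Objective 3 ends at 12 months. The plan acknowledges late onset under Potential challenges but does not carry it into the sample size.
- **Outcome.** The sample size concerns any of six sequela types; the comparison of proportions concerns two of them.

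Objective 3 is a primary objective, and the plan expects its results to inform discussion of hearing and CMV screening. If the comparison is null, readers will look to the 80% to judge how informative it is.

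**Working it through.** **Inputs from the plan.** Case rate 17%, control rate 1%, allocation 1:2, power 80%, loss 10%, 42 + 84 enrolled. Evaluable: 42 × 0.9 = 37.8, about 38; 84 × 0.9 = 75.6, about 76. The significance level is not stated for Objective 3; two-sided 5% is assumed, in line with the 95% intervals.

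**Step 1: the plan's own figure.** The usual formula for two proportions, with k = 2 controls per case and p̄ = (p1 + k·p2)/(1 + k), is

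n1 = [1.96·√(p̄(1−p̄)(1+1/k)) + 0.842·√(p1(1−p1) + p2(1−p2)/k)]² / (p1−p2)²

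With p1 = 0.17 and p2 = 0.01, p̄ = 0.0633 and n1 = 32.1, so 33 cases; 33/0.9 = 36.7, so 37 cases and 74 controls. With a continuity correction the figure is 41 cases, or 46 after loss. The stated 42 lies between 37 and 46. It also equals the expected screening yield in section 3.3 (31 + 11). The exact figure is not reproduced, but nothing here turns on the arithmetic.

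**Step 2: who the controls are.** Section 3.3 expects 31 of about 42 cases to be HIV exposed: 31/42 = 74%. Matching on HIV exposure makes about three quarters of the controls HIV exposed. They are also matched on gestational age within 2 weeks, and no criterion excludes perinatal events.

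**Step 3: power when the rates move.** For the planned test, power was computed exactly. The binomial probabilities of all outcomes (a events in 38 cases, b in 76 controls) with |Z| ≥ 1.96 were summed, where

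Z = (a/38 − b/76) / √(p̂(1−p̂)(1/38 + 1/76)) and p̂ = (a+b)/114.

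Fisher's exact test is shown for comparison. The groups are treated as independent, as the Z test does.

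| Cases | Controls | Z test | Fisher |
|---|---|---|---|
| 17% | 1% | 92% | 90% |
| 17% | 2% | 83% | 80% |
| 17% | 3% | 73% | 69% |
| 17% | 5% | 54% | 49% |
| 12.75% | 1% | 80% | 75% |
| 10% | 1% | 66% | 59% |
| 10% | 3% | 35% | 31% |
| 25% | 5% | 86% | 83% |

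Only the first row uses the plan's rates. The others are assumptions, because the documents give no 12-month rates for infants like those enrolled. The 12.75% is three quarters of 17% (0.75 × 17). The last row shows the effect if the composite raises both rates.

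The approximate formula at 38 + 76 gives 85% for 17% vs 1% without continuity correction and 77% with it, so the method needs to be named alongside any figure.

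**Step 4: powered and tested outcomes.** The composite has six components: hearing loss, developmental deficit, ocular abnormality, abnormal imaging, microcephaly and seizures. The Z test uses the first two, repeated at each visit. The sample-size section gives no rate for that narrower pair.

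**The case against.** The strongest reply is that power is always conditional on stated rates, that the plan states them, and that it warns openly that 12 months may be too short and no difference may be seen. It also plans 95% confidence intervals. All of that stands. It limits the harm but does not align the inputs with the design.

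Several stronger readings are tempting and are not supported:

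- *Both rates are too optimistic.* This is plausible for controls. For cases it is not shown: stopping at 12 months would lower the rate, but imaging abnormality and microcephaly count towards the composite and could offset that. At 25% vs 5%, power would be 86%.
- *80% power requires about 17% in cases and no more than 2% in controls.* The table contradicts this: 12.75% vs 1% gives about 80%, and 25% vs 5% gives more.
- *The plan's other figures prove that 17% is a lifetime rate.* Weighting the section 1.2 rates gives 0.10 × 40% + 0.90 × 14% = 16.6% at the low end and 0.15 × 58% + 0.85 × 14% = 20.6% at the high end. These rates carry no age either, so they say nothing about timing. The shared citation with the 6-year advice suggests a mismatch but does not prove one.
- *A null result will be presented as evidence of no harm.* The plan does not say so, and its own caveat points the other way.

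Finally, the calculation and the case definitions are referred to Appendices 9 and 11, which are not in the text available here. Appendix 9 may already vary the sequelae rates, so the absence of a sensitivity table cannot be claimed.

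**Conclusion.** The point holds as a mismatch of inputs and outcome, not as an arithmetic error and not as proof that the study is underpowered. The control rate comes from a lower-risk group than the one enrolled; the case rate has no age attached while follow-up ends at 12 months; and the comparison of proportions is narrower than the outcome used for the sample size.

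The consequence is sensitivity. Under the planned test, a control rate of 3% instead of 1% takes power from about 92% to 73%; a case rate of 10% takes it to 66%; both together take it to 35%. Higher rates in both groups could leave it above 80%. These figures assume two-sided 5%, 38 and 76 evaluable infants, independent groups and illustrative rates. The direction is reasonably clear for controls and open for cases.

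**What to change.** 1. In the Objective 3 analysis table, make the main case-control comparison the cumulative proportion of infants with any of the six listed sequelae by 12 months. Keep hearing impairment and developmental deficit as secondary comparisons. The tested and powered outcomes then agree.
2. In section 3.4 (Sample size), state the power as conditional on 12-month rates in cases and in controls like those enrolled. Name the test, the significance level and the evaluable numbers, and give the Z-test range above, including a row with higher rates in both groups. Label every rate other than 17% and 1% as an assumption. If Appendix 9 already has such a range, refer to it and align it with the 12-month composite.

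The cost is wording and one analysis change, with no extra participants. The stated power will look less favourable. The composite also needs a rule for infants who miss some assessments, because not every investigation is done at every visit.
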